11.0 STATISTICAL AND ETHICAL CONSIDERATIONS

11.1 Sample Size and Study Duration

A minimum of 4 and a maximum of 18 evaluable patients will be required to complete the dose confirmation part of the study using a rolling 6 design. Once the MTD or recommended Phase 2 dose has been defined, up to 6 additional patients may be enrolled to acquire PK data in a representative number of young patients (i.e. patients < 12 years old). Therefore, a maximum of 23 patients are anticipated to be enrolled in this study allowing for two dose levels, PK expansion, and 20% inevaluability. Review of the enrollment rate into previous COG new agent studies indicates that 1-2 patients per month are available, which will permit completion of the study within 12-23 months.

In the unlikely event that two DLTs of different classes occur, then expansion to 12 patients at that dose level may be considered if ALL of the following conditions are met: 1) one of the DLTs does not appear to be dose and/or drug-related, 2) the Adverse Effects are readily reversible, 3) the study chair, DVL statistician, DVL committee chair or vice chair, and IND sponsor all agree that expansion of the cohort is acceptable (see [Section 11.2.2](#)). In this case, the absolute maximum number of patients would be 38 patients allowing for 12 patients at each of two dose levels, 6 patients for PK expansion, and 20% inevaluability. This would be completed within 19-38 months.

Given the novelty of this regimen, enhanced monitoring for DLTs will be performed in the first 3 patients. If 2 DLTs are observed then the dose will be de-escalated to DL-1. If 1 DLT is observed in the first 2 patients then a period of 30 days must have elapsed between the first dose of MLN4924 (pevonedistat) in the 3rd patient prior to enrolling the 4th patient.

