3.10 Dose Assignment

The dose level will be assigned via OPEN at the time of study enrollment.

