NOTE: Central venous access in the form of a double lumen Broviac or Hickman is highly recommended.

	Day 0	1	2	3	4	5	6	7	8	9	10	11-34	35
IT Cytarabine (all patients)	X												
Azacitidine		X	X	X	X	X							
MLN4924 (Pevonedistat)		X		X		X							
Fludarabine							X	X	X	X	X		
Cytarabine							X	X	X	X	X		
IT Cytarabine OR ITT* (CNS2/3)									X*			X*	

*For patients with CNS 2/3 status, IT cytarabine or ITT should be administered 2x/weekly until the CNS is clear of blasts on 2 consecutive LPs, with a minimum of 4 IT cytarabine/IT triple doses administered. This should begin on Day 8 and should be repeated 2x/weekly with not less than 3 days between doses, thus any necessary subsequent doses should be given starting on Day 11. Days of therapy may vary depending on scheduling.

A cycle of therapy is considered to be 35 days. A cycle may be repeated for a total of 2 cycles, up to a total duration of therapy of approximately 4 months.

Drug doses of MLN4924 (pevonedistat), azacitidine, fludarabine, and cytarabine should be adjusted based on the BSA calculated from height and weight measured within 7 days prior to the beginning of each cycle. Drug doses of intrathecal cytarabine and intrathecal triples should be based on the age at the time of administration.

See [Appendix VIII](#) for Therapy Delivery Maps for each cycle.

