5.4.2 Intra-Patient Escalation

Intra-patient dose escalation is not allowed.

5.5 **Grading of Adverse Events**

Adverse events (toxicities) will be graded according to the NCI Common Terminology Criteria for Adverse Events (CTCAE) version 5.0. All appropriate treatment areas should have access to a copy of the CTCAE version 5.0. A copy of the CTCAE version 5.0 can be downloaded from the CTEP website (http://ctep.cancer.gov/protocolDevelopment/electronic_applications/ctc.htm). Any suspected or confirmed dose-limiting toxicity should be reported immediately (within 24 hours) to the Study Chair.

5.6 **Definition of Dose-Limiting Toxicity (DLT)**

DLT will be defined as any of the following events that are possibly, probably or definitely attributable to protocol therapy. The DLT observation period for the purposes of dose-confirmation will be the first cycle of therapy.

Dose limiting hematological and non-hematological toxicities are defined differently.

5.6.1 Non-hematological dose-limiting toxicity:

5.6.1.1 All Grade 3 or greater non-hematological toxicity not clearly related to the underlying disease and attributable to protocol therapy will be considered a DLT except:

- Grade 3 or 4 elevation of ALT/AST that returns to Grade ≤ 1 within 14 days. NOTE: For the purposes of this study the ULN for ALT is defined as 45 U/L regardless of baseline and for AST is defined as 50 U/L regardless of baseline. See [Appendix III](#) for values that represent thresholds between CTCAE grades.

THIS PROTOCOL IS FOR RESEARCH PURPOSES ONLY, SEE PAGE 1 FOR USAGE POLICY

- Grade 3 or 4 electrolyte abnormalities that resolve, with or without supplementation intervention, to \leq Grade 2 within 72 hours. Electrolyte supplementation is encouraged.
- Grade 3 arthralgia/myalgia that returns to Grade \leq 2 within 5 days on analgesics
- Grade 3 or 4 fever, febrile neutropenia, or infection with or without hospitalization
- Grade 3 tumor lysis syndrome
- Alopecia
- Grade 3 maculo-papular or morbilliform rash that resolves to \leq Grade 2 within 7 days
- Grade 3 mucositis that resolves (with or without supportive care) to \leq Grade 2 within 14 days
- Grade 3 fatigue or anorexia responsive to supportive care within 7 days
- Grade 3 nausea, vomiting, and/or diarrhea responsive to supportive care within 72 hours
- Early intervention with TPN or enteral tube feeding for anorexia, nausea, or concern for poor nutritional status

5.6.2 Hematological dose-limiting toxicity:

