Hematological dose limiting toxicity attributable to protocol therapy is defined as failure to recover to a peripheral ANC $> 500/\text{m}^3$ and platelets $> 20,000/\text{mm}^2$ by 50 days from the start of fludarabine and cytarabine administration, not due to presence of leukemia or severe infection (defined as Grade ≥ 3).

- **NOTE:** Grade 3 or 4 febrile neutropenia will not be considered a dose-limiting toxicity

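### After a DLT in one of the first two patients, the 30-day hold on the 4th patient ends 5 days before the 3rd patient's 35-day DLT observation period does

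*Combined protocol and SAP*

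**What the plan says.** Section 11.1 adds a safeguard for the first 3 patients because the regimen is new. It has two parts. The first is a de-escalation rule: "If 2 DLTs are observed then the dose will be de-escalated to DL-1". The second is a hold on the next enrollment, which applies when 1 of the first 2 patients has had a DLT: "then a period of 30 days must have elapsed between the first dose of MLN4924 (pevonedistat) in the 3rd patient prior to enrolling the 4th". The sentence contains the word for an interval between two events but names only one of them. The natural reading is 30 days counted from the 3rd patient's first dose.

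Four other places bear on it:

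- Section 5.6: "The DLT observation period for the purposes of dose-confirmation will be the first cycle of therapy".
- Section 5.1: "A cycle of therapy is considered to be 35 days".
- Section 3.10: "The dose level will be assigned via OPEN at the time of study enrollment".
- Section 5.6.2: the hematologic DLT is failure of count recovery "by 50 days from the start of fludarabine and cytarabine administration". By Section 5.1 those drugs start on Day 6. Section 2.1 also uses 50 days, but counts them from the start of therapy.

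No section extends the hold or requires the 3rd patient to finish Cycle 1 before the 4th is enrolled.

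**The concern.** The hold is triggered by a first DLT, is timed from the 3rd patient's first dose, and directly follows the rule that a second DLT means de-escalation. The evident reason to wait is to learn whether the 3rd patient supplies that second DLT. A 30-day wait does not cover the 35-day period in which that DLT can be counted.

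At stake is enrollment at a dose level that may be about to close. From Day 31 of the 3rd patient's Cycle 1, a 4th patient can be assigned Dose Level 1 while the 3rd is still under DLT observation. The situation is the one for which Section 11.1 makes a special exception to ordinary rolling enrollment, so the exception should match the protocol's own observation period.

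**Working it through.** **The stated figure.** The 30 days are given without a derivation, so there is no formula to reproduce. The enrollment ceilings in the same section do reproduce: 18/(1 − 0.20) = 22.5, rounded up to 23, and 30/(1 − 0.20) = 37.5, rounded up to 38. The point does not depend on them.

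**Day count.** Take the 3rd patient's first pevonedistat dose as Day 1.

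| Event | Source | Elapsed days | Shortfall of the hold |
|---|---|---|---|
| Hold ends; 4th patient may enroll (Day 31) | 11.1 | 30 | – |
| DLT observation period ends | 5.6, 5.1 | 35 | 35 − 30 = 5 |
| Hematologic DLT read, 50 days from start of therapy | 2.1 | 50 | 50 − 30 = 20 |
| Hematologic DLT read, 50 days from Day 6 (Day 56) | 5.6.2, 5.1 | 55 | 55 − 30 = 25 |

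Section 3.9 allows up to 5 calendar days from enrollment to the projected start of therapy. The 4th patient's first dose could therefore fall anywhere from Day 31 to Day 36. That interval is a maximum with no minimum, and the dose level is already assigned at enrollment, so it does not close the gap.

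**How often it would matter.** Let p be the true DLT rate per patient, with patients independent, and f the share of DLTs declared only after Day 30. The documents give neither p nor f for this regimen; both are assumptions.

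- Chance of entering the branch (exactly 1 DLT in 2 patients): 2p(1 − p) = 0.32, 0.42 and 0.48 for p = 0.2, 0.3 and 0.4.
- Chance of entering it and then having a late DLT in the 3rd patient: 2p(1 − p) × p × f.

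| p | f = 0.10 | f = 0.25 | f = 0.50 |
|---|---|---|---|
| 0.2 | 0.6% | 1.6% | 3.2% |
| 0.3 | 1.3% | 3.2% | 6.3% |
| 0.4 | 1.9% | 4.8% | 9.6% |

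Once the trial is in the branch, the chance of a late second DLT is p × f: from 0.2 × 0.10 = 2% to 0.4 × 0.50 = 20%.

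A lower anchor is the adult azacitidine combination in Section 2.3.1: DLTs in 2 of 55 patients at 20 mg/m², so p ≈ 0.036. Then 2p(1 − p) ≈ 0.07, and the joint chance is about 0.03% (f = 0.10) to 0.13% (f = 0.50). The population and backbone differ, so this only shows how strongly the result depends on p.

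**How many patients.** At the stated 1–2 patients per month (30 days), 5 days bring 5/30 × (1 to 2) = 0.17 to 0.33 new patients, and 25 days bring 0.83 to 1.67. A patient already waiting when the hold lifts would add to this.

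**The case against.** The strongest reply is that nothing here is a contradiction. Section 11.1 never says that the hold runs until the 3rd patient's DLT status is complete. A rolling six design enrolls patients while earlier ones are still under observation, and this clause only removes exposure that the base design would allow. On that view a partial stagger is a legitimate choice.

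Part of this stands. The purpose of the hold is inferred, and the hold does useful work. Scheduled systemic dosing ends on Day 10, so Day 30 is 20 days later. Suspected DLTs go to the study chair within a day (Section 5.5), and study data are reviewed on a weekly call (Section 13.7.2). A DLT that declares itself by Day 30 can therefore be acted on. A reader might infer that the hold ends before anything useful can be known; the documents do not support that. What cannot be known by then is that the 3rd patient is free of DLT.

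The rolling design does not dispose of the point, however. The clause is an explicit exception to rolling enrollment, triggered by a first DLT and placed beside the 2-DLT rule. No reason is given for stopping it 5 days short.

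A reader might also infer that up to three children (the 4th to 6th patients) would be exposed to no purpose. Three is a ceiling: at the stated accrual, usually no more than one or two would enroll in the gap. Nor would their data be wasted, since they would still contribute PK and toxicity data. Sections 11.1 and 11.2.2 also allow two DLTs of different classes to lead, under conditions, to expansion of the cohort rather than de-escalation.

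**Conclusion.** The point holds in a limited form. On the protocol's own figures, the hold ends 5 days before the 3rd patient's DLT observation period does, and the 4th patient's dose level can be fixed in that interval. This part needs no assumption beyond the inferred purpose of the hold.

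The practical size is modest. The joint chance of about 0.6% to 10% rests on assumed values (p of 0.2 to 0.4, f of 0.10 to 0.50, independent patients) and would be lower at a DLT rate like that of the adult combination. It would be wrong to read the 0.32 to 0.48 for entering the branch as the chance of harm. That figure also rests on an assumed p, and harm further requires a late DLT in the 3rd patient and an enrollment in the gap.

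A reader might go further and conclude that the hold must run to the hematologic time point. The documents do not settle this. Section 5.6 limits DLT observation to Cycle 1, Section 5.6.2 sets a 50-day hematologic criterion that does not fit inside 35 days, and Sections 2.1 and 5.6.2 start the 50 days from different events. The 20- or 25-day shortfall depends on how that conflict is resolved; the 5-day shortfall does not.

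**What to change.** In Section 11.1, replace the 30-day count with the protocol's own observation period: after 1 DLT in the first 2 patients, the 4th patient is not enrolled until the 3rd has completed Cycle 1 (35 days) or has had a DLT, in which case the 2-DLT rule applies. This also repairs the missing endpoint in the sentence. If the shorter stagger is intended, Section 11.1 should say so and give the reason.

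Separately, reconcile Sections 2.1, 5.6 and 5.6.2 on when the hematologic DLT is read, and then state whether the hold must cover it. The choice is the sponsor's.

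The cost is one sentence and a one-time accrual delay of about 5 days, only if one of the first two patients has a DLT. Extending the hold to the hematologic time point would make the delay 20 or 25 days, depending on the reconciliation.

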11.2 Definitions

11.2.1 Evaluable For Adverse Events

Any patient who receives at least 2/3 doses of MLN4924 (pevonodistat) during Cycle 1 or who experiences a dose-limiting toxicity is considered evaluable for Adverse Events. In addition, for the dose-confirmation portion during Cycle 1, patients must receive at least 85% of the prescribed dose per protocol guidelines and must have the appropriate toxicity monitoring studies performed to be considered evaluable for dose limiting toxicity. Patients who do not have DLT and are not considered evaluable for toxicity will be replaced.

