6.2 Dose Modifications for Non-Hematological Toxicity

6.2.1 Patients will have ALT/AST/bilirubin evaluated prior to each planned dose of MLN4924 (pevonedistat) in order to determine whether the scheduled dose

should be administered. It is anticipated that ALT and AST may be elevated for approximately 48 hours following the end of the 1st MLN4924 (pevonedistat) infusion.

NOTE: See [Appendix III](#) for toxicity grading table.

If a patient experiences > Grade 3 elevation of ALT/AST on or after Cycle 1, Day 1 then the Cycle 1, Day 3 MLN4924 (pevonedistat) dose should not be given. If ALT/AST returns to \leq Grade 1 or baseline values by Day 5 then the patient should receive their Day 5 MLN4924 (pevonedistat) dose and this will not be considered a DLT. If ALT/AST does not return to \leq Grade 1 or baseline values by Day 5 then MLN4924 (pevonedistat) should be held and this will be considered a DLT. Persistent elevations of ALT/AST > Grade 2 beyond 2 days between any other doses after Cycle 1, Day 1 will be considered a DLT.

6.2.2 Patients who experience a dose limiting toxicity during cycle 1 that resolves to baseline or < Grade 1 at the time of next cycle can proceed with the next cycle at dose level -1.

6.3 **Modifications and Supportive Care Recommendations for Toxicity Related to Protocol Therapy (Cycle 1 and Cycle 2)**

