11.3 Dose Confirmation and Determination of MTD/RP2D

The rolling six phase 1 trial design will be used for the conduct of this study.³² There is no dose escalation beyond DL1 (20 mg/m²); but the R6 logic will be used to determine the MTD/RP2D. DL1 will be defined as the RP2D if there are less than or equal to 1 patient(s) with a DLT among up to six evaluable patients. Otherwise, DL-1 will open to accrual of up to six evaluable patients. DL-1 will be defined as the MTD/RP2D if there are less than or equal to 1 patient(s) with a DLT among six evaluable patients. Otherwise, DL-1 will have exceeded the MTD and the study will close to accrual without having defined an MTD/RP2D.

In addition to determination of the RP2D/MTD, a descriptive summary of all toxicities will be reported.

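### Sections 5.6.1.1, 6.2.1 and 6.3.5 give opposite DLT answers for the same ALT/AST course; separately, no stated patient set ensures that toxicities of early stoppers are summarised

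*Combined protocol and SAP*

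**What the plan says.** **DLT status of ALT/AST elevations**

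- Section 5.6.1.1 makes Grade 3 or higher attributable non-hematological toxicity a DLT, with exceptions. One exception is "Grade 3 or 4 elevation of ALT/AST that returns to Grade" 1 or lower within 14 days.
- Section 6.2.1 omits the Cycle 1 Day 3 pevonedistat dose when ALT/AST is, as printed, above Grade 3. If values are back to Grade 1 or baseline by Day 5, "then the patient should receive their Day 5 MLN4924 (pevonedistat) dose and this will not be considered a DLT". If they are not, pevonedistat "should be held and this will be considered a DLT". A further sentence makes elevations above Grade 2 that persist beyond 2 days between other doses a DLT.
- Section 6.3.5 says that ALT, AST or bilirubin of Grade 3 or higher, not back to Grade 1 or baseline before the next pevonedistat dose, means that the dose is held and a DLT is counted.
- Section 11.2.2 defines the MTD through DLTs and points to Section 5.6. Section 11.3 accepts dose level 1 as the RP2D with at most one DLT among up to six evaluable patients.

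**Who is summarised**

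- Section 11.2.1 defines one AE-evaluable set: "Any patient who receives at least 2/3 doses of MLN4924 (pevonodistat) during Cycle 1 or who experiences a dose-limiting toxicity". For DLT evaluability in dose confirmation, "patients must receive at least 85% of the prescribed dose per protocol guidelines". It adds: "Patients who do not have DLT and are not considered evaluable for toxicity will be replaced".
- Section 11.3 promises that "a descriptive summary of all toxicities will be reported", without naming the patients.

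**The concern.** A DLT rule has to give one answer for one clinical course. Here the answer depends on which section the assessor opens, and the count that decides the RP2D is small enough for one patient to change it. The courses in question are not far-fetched. Section 6.2.1 itself states: "It is anticipated that ALT and AST may be elevated for approximately 48 hours following the end of the" first infusion. It gives no grade, but the pre-Day 3 blood draw falls inside that window.

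The secondary matter is aim 1.1.2, the description of toxicities. A patient who receives one of three doses and has no DLT is outside the only AE-evaluable set and is replaced. Section 10.1 allows such an exit through refusal or physician decision. If the toxicity summary were run on the Section 11.2.1 set, it would describe patients partly selected for having tolerated treatment.

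**Working it through.** **Inputs.** ALT grades are from Appendix III (ULN 45 U/L): Grade 1 up to 135, Grade 3 from 226 to 900, Grade 4 above 900. The entry limit in Section 4.1.5.2 is 2.5 × 45 = 112.5 U/L, below 135, so the words on baseline in Sections 6.2.1 and 6.3.5 do not change the answers for ALT. Attribution to protocol therapy is assumed throughout.

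**Step 1: the three sections side by side.**

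| ALT course | 5.6.1.1 | 6.2.1 | 6.3.5 |
|---|---|---|---|
| A: above 900 before Day 3, at most 135 by Day 5 | not a DLT | not a DLT | DLT |
| B: above 900 before Day 3, unrecovered at Day 5, at most 135 within 14 days | not a DLT | DLT | DLT |
| C: 226 to 900, unrecovered before the Day 3 dose, at most 135 within 14 days | not a DLT | Day 3 rule not triggered as printed; the rule on elevations above Grade 2 beyond 2 days may apply | DLT |

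The comparison sign in Section 6.2.1 may have been altered in text extraction: the same resolution sentence is printed with different signs in Sections 6.2.2 and 6.3.5. If the trigger were Grade 3 or higher, course C would be judged like A or B, depending on recovery by Day 5, and would still be in conflict.

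**Step 2: timing.** With dosing at the same clock time on Days 1 and 3 and a 60-minute infusion, the pre-Day 3 draw is at most about 48 − 1 = 47 hours after the first infusion ends.

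**Step 3: the plan's own boundary.** Section 11.2.2 requires fewer than one-third with DLT. 1/6 = 16.7% passes and 2/6 = 33.3% does not, which matches the limit of one DLT in Section 11.3. After PK expansion, 3/12 = 25% passes and 4/12 = 33.3% exceeds the MTD.

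**Step 4: effect of one disputed patient in a cohort filled to six.** Let d be the DLT rate from other causes and X the number of DLTs among the other five patients.

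- Counted as a DLT: the total is 1 + X, so the dose is accepted only if X = 0.
- Kept as a non-event: the total is X, so the dose is accepted if X ≤ 1. The decisions differ when X = 1, with probability 5d(1−d)^4.
- Replaced: the decisions differ when X = 1 and the replacement has no DLT, with probability 5d(1−d)^5.

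| d (assumed) | kept | replaced |
|---|---|---|
| 0.10 | 5 × 0.1 × 0.6561 = 0.328 | × 0.9 = 0.295 |
| 0.20 | 5 × 0.2 × 0.4096 = 0.410 | × 0.8 = 0.328 |
| 0.30 | 5 × 0.3 × 0.2401 = 0.360 | × 0.7 = 0.252 |

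These probabilities are conditional on one such patient occurring. The documents give no rate for courses A to C, and the values of d are assumptions.

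**Step 5: the AE set.** One of three doses is 33%, below two-thirds. Without a DLT, the patient is outside the set. One such patient beside six evaluable patients is 1/7 = 14% of those treated.

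**The case against.** **Section 6 is the more specific text.** Its rules could be read as additions to Section 5.6, which would make B and C DLTs, and Section 6.2.1 as a Cycle 1 carve-out from Section 6.3.5, which would settle A. This is a reasonable reading, but nothing states it, and Section 11.2.2 points to Section 5.6. As printed, it would also make a Grade 3 elevation unrecovered at Day 3 a DLT while a Grade 4 elevation recovered by Day 5 is not.

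**DLTs are reviewed weekly.** Sections 13.7.2 and 14.4.2 provide joint review by the study chair, program leadership and the statistician. That makes decisions consistent within the group, but it gives the group no rule to apply.

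**The AE set may do no harm.** This objection largely stands. Section 11.3 speaks of all toxicities and does not limit itself to the Section 11.2.1 set. Section 10.1 requires Cycle 1 observations and AE reporting after removal from therapy. A reader might infer that the hepatic hold rules push one-dose patients out of the AE set. They do so only if Section 5.6.1.1 overrides both 6.2.1 and 6.3.5, since each of those makes the unrecovered hold a DLT and so puts the patient in the set.

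**Dose loss and terminology.** A reader might also count the missing summary of held doses as an error, because aim 1.1.1 is tolerability and feasibility. Section 5.1 gives the primary purpose as the safety and toxicity profile and a phase 2 dose, so such a table is useful but not required. Nor is the replacement rule's reference to toxicity a real gap, since Section 5.5 treats adverse events and toxicities as the same thing.

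**Conclusion.** The main point holds on the text alone: courses A, B and C each receive conflicting DLT answers, and no precedence is stated. One disputed patient can decide between accepting dose level 1 (1 of 6) and opening dose level −1 (2 of 6), or considering expansion to 12 if the conditions in Section 11.2.2 are met. At dose level −1, the same step decides whether the study closes without an RP2D. After PK expansion it decides between 3 and 4 of 12. Given one such patient and an assumed other-cause DLT rate of 10% to 30%, the chance that the reading changes the six-patient decision is about 0.25 to 0.41. It would go too far to infer that the RP2D is likely to be wrong, because the frequency of these courses is unknown.

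The secondary point is a clarification. Toxicities of patients who stop after one dose without a DLT could be left out of the report for aim 1.1.2, but the plan does not say that they will be, and the data are collected.

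**What to change.** 1. **Reconcile Sections 5.6.1.1, 6.2.1 and 6.3.5** so that one rule says when an ALT/AST elevation or hold is a DLT, and confirm the grade sign in Section 6.2.1. Which rule should apply is a clinical decision and is not proposed here. This needs a protocol amendment but no new data.

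2. **State in Sections 11.2.1 and 11.3** that the descriptive toxicity summary covers all patients who received at least one dose of pevonedistat, and that the evaluable set is used only for counting DLTs. This costs a sentence in each section, since AE data are already collected after removal under Section 10.1.

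3. **Optional, not part of the error.** In the same amendment, say which drug or drugs the 85% covers and whether a protocol-directed hold counts against it. If pevonedistat is the denominator, 0.85 × 3 = 2.55, so two of three doses (67%) fall short. This affects who is DLT-evaluable, so it is more than a wording change. A summary of Cycle 1 pevonedistat doses given or held would also help. The therapy delivery maps have a comments field for held doses but do not ask for reasons, and Section 14.1 classes the maps as non-computerized, so some abstraction would be needed.
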